7.1.3.3 ADHD-RS-IV

Continuous summary statistics will be presented for the ADHD-RS-IV Total, Inattention, and Hyperactivity-Impulsivity scores at each visit from baseline through Visit 7 and for the change from baseline to each subsequent visit for the FAS. The ADHD-RS-IV Total and subscale scores will also be plotted by visit for the FAS.

The ADHD-RS-IV Total and subscale scores at Visits 6 and 7 will be analyzed in a similar way to the primary efficacy analysis, with the exclusion of timepoint from the model. Raw means, LS means, differences in LS means, and 95% CI for the difference between treatment groups, p-values, and model results will be presented for each variable.

7.1.3.4 CPRS-R:S

Continuous summary statistics will be presented for the CPRS-R:S Total, Oppositional, Cognitive Problems/Inattention, Hyperactivity, and ADHD Index scores at each visit from Visit 1 through Visit 7 for the FAS. The CPRS-R:S Total and subscale scores will also be plotted by visit for the FAS.

The CPRS-R:S Total, Oppositional, Cognitive Problems/Inattention, Hyperactivity, and ADHD Index scores at Visits 6 and 7 will be analyzed in a similar way to the primary efficacy analysis, with the exclusion of timepoint from the model. Raw means, LS means, differences in LS means, and 95% CI for the difference between treatment arms, p-values, and model results will be presented for each variable.

7.1.3.5 CGI

Categorical summary statistics will be presented for the CGI-S scores at baseline for the FAS. Categorical summary statistics will also be presented for the CGI-I scores at each visit after baseline for the FAS. The categorical CGI-I summaries will be presented both for all categories of the scale and for the dichotomized version of the scale defined in Section 4.2.5. The percentages of subjects who improved according to the dichotomized version of the scale will also be plotted by visit for the FAS.

Differences between the treatment arms in the dichotomized versions of the CGI-I scores at Visits 6 and 7 will be analyzed by using McNemar's test. In order to adjust for a potential period effect, the Mainland-Gart test, which is a test of sequence versus period preference, will also be performed. Finally, Prescott's test, which extends the Mainland-Gart test by including subjects who show no preference between the two periods, will also be conducted. Test statistics and p-values for the difference between the treatment arms will be presented for each test.

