	
analog classroom sessions in the laboratory school setting). Visit 7 will also serve as the End of Study Visit.
 
Following Screening Period and Washout Period (if applicable), eligible subjects will enter the open-label Dose-Optimization Period, during which they will begin receiving d-ATS followed by evaluation for efficacy and tolerability of that dosage approximately 4 days later. Dosage will be initiated at 5 mg/ 4.76 cm^2 d-ATS and adjusted to the next available dose at weekly intervals, until optimal dose is reached. Optimal dose will be defined as the dose that will produce a reduction in ADHD RS-IV score <math>\geq</math> 30% and CGI-Improvement (CGI-I) score of 1 or 2 and has tolerable side effects. Tolerability will be determined by the investigator, based on review of AEs and clinical judgment. Once reached, the optimal dose will be maintained for the remainder of the Dose-Optimization Period. Subjects will be discontinued if they are unable to tolerate d-ATS or cannot reach their optimal dose by Week 5. If the subject has reached their optimal dose, then at the discretion of a medically qualified investigator, one dose reduction per participant may occur during the dose optimization period for safety reasons. However if the current dose is intolerable and the subject has never reached their optimal dose, the subject would be discontinued from the study. A dose increase may occur at visit 4 if no prior dose has met criteria for optimal response and the current dose is well tolerated as deemed by a medically qualified investigator. The dose used during the week 5 visit will be the dose that the subject is randomized to during the Double-Blind Treatment Period. During Visit 5 (Day 35), subjects will attend a half-day practice laboratory school with analog classroom sessions to become familiar with classroom schedules and procedures. Three SKAMP assessments will be performed, and 3 practice PERMP tests will be given during the practice session. Practice laboratory classroom periods will be 30 minutes in length to allow sufficient time for SKAMP and PERMP ratings and transition times.
 
Following dose optimization, subjects will enter the two-week double-blind treatment period. Subjects will be randomized to receive daily d-ATS treatment (at the optimized dose) for one week followed by daily placebo patches (identical in appearance to d-ATS) for one week, or vice versa. During the Double-Blind Period, for the first six days of each week study drug will be administered by the subject/parent/caregiver. On the last day of each week (analog classroom days) the patches will be applied in the clinic by study staff at

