**Double-Blind Treatment Period [Day 36 to Day 49; Visit 6 (Day 42) and Visit 7 (Day 49)]:**

Subjects who have reached an optimal dose will be randomized at Visit 5 to receive double-blind treatment. Administration of study medication will begin on Day 36 and continue up to Day 49 (end of Week 7). During Week 6 subjects will receive study patches in accordance with the randomization schedule and during Week 7 subjects will cross-over to receive the other study treatment per the randomization schedule. Subjects/parents/caregivers will be instructed to apply study patches to the hip once daily in the morning at approximately 8:00 am. Patches will be removed after 9 hours. Each day a new patch will be applied to the opposite hip. Subjects will be instructed to continue completing the daily dosing diary and the daily dermal diary. Subjects will return to the clinic for evaluations and analog classroom sessions in the laboratory classroom setting on Visit 6 (Day 42) and Visit 7 (Day 49). Site personnel will contact subjects by telephone on Day 39 and Day 46. All end of study procedures will be completed for subjects who are early discontinuations from the study.

**Follow-Up:** A safety follow-up by telephone 7- 10 days (Visit 8, Day 56 + 3 days) after last dose of study drug.

**Sample Size:** Sufficient number of subjects with ADHD will be screened to randomize approximately 90 subjects. Assuming a 20% dropout rate, it is expected that 74 subjects will complete the study. The Full Analysis Set population (FAS) will be used as the primary population for analysis of efficacy endpoints and is defined as subjects who have taken at least one dose of study medication.

Amendment 4: Version 5.0 May-08-2013

Amendment 3: Version 4.0 December-11-2012

Amendment 2: Version 3.0 October-31-2012

Amendment 1: Version 2.0 August-02-2012

Final Protocol May-25-2012

**Study Duration:** The duration of the study will be approximately 56 days for each individual subject (not including screening and washout).

**Study Population:** The study population will consist of children and adolescents 6 to 17 of age, who have been diagnosed with ADHD.

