6. ANALYSIS POPULATIONS

6.1 FULL ANALYSIS SET

The full analysis set (FAS) includes all consented and randomized subjects who have taken at least one dose of study medication. The FAS population will be used as the primary population for analysis of efficacy endpoints.

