7. STATISTICAL METHODS

Summaries will be presented for the SP population for all subjects combined during the Dose-Optimization Period of the study. During the double-blind Treatment Period of the study, summaries will be presented for the FAS, Completers, and SP populations by treatment (i.e., d-ATS and placebo, with all d-ATS dose levels combined), and some tables by treatment and treatment sequence. Subjects are intended to receive both treatments during the double-blind cross-over period of the study, so summaries for Visits 6 and 7 will be combined, with subjects contributing data to both treatment columns for the combined time point. As a result, the numbers of subjects in each treatment arm in the header of these summaries will reflect the total number of subjects receiving the treatment, and the number of subjects contributing data for each visit will be presented in the body of the table.

Early termination visits will be mapped to the next scheduled visit for inclusion in summary tables, where appropriate. For example, a subject who terminates after Visit 3 (e.g., has assessments at Visits 1 - 3 and early termination assessments) would have assessments from early termination mapped to the next scheduled visit for each assessment. Different assessments may be mapped to different visits; in this example, most assessments would be mapped to Visit 4, ECG would be mapped to Visit 5 as no ECG assessments are scheduled to be performed at Visit 4. This mapping is considered part of the observed values, and will be conducted before any summaries or analyses are performed on observed values. Similarly, it will be conducted before any scoring algorithm is applied. Listings will present early termination data as the mapped visit, as well as under 'ET' Visit as well.

Unless otherwise noted, categorical variables will be summarized using counts and percentages. Percentages will be rounded to one decimal place, except 0% and 100% will be displayed without any decimal places. Continuous variables will be summarized using the number of observations (n), mean, standard deviation (SD), median, minimum, and maximum. All analyses will use SAS® version 9.1 or higher.

All raw data will be presented to the original number of decimal places. The means and medians will be presented to 1 more decimal place than the raw data. The standard deviations will be presented to 2 more decimal places than the raw data.

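### Open-label efficacy summaries at Visits 1 to 5 are specified on the FAS, which is selected on response and tolerability, while SAP 7 assigns that period to the Safety population

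*SAP*

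**What the plan says.** **The tables.** SAP 7.1.3.3 asks for ADHD-RS-IV summaries from baseline to Visit 7 and "for the change from baseline to each subsequent visit for the FAS". SAP 7.1.3.4 asks for CPRS-R:S summaries "at each visit from Visit 1 through Visit 7 for the FAS". SAP 7.1.3.5 treats CGI-I the same way, in full categories and as responder/non-responder: "Categorical summary statistics will also be presented for the CGI-I scores at each visit after baseline for the FAS". Each section adds a plot by visit on the FAS. SAP 7.1 places open-label and double-blind results in one table and leaves the placebo column empty for dose optimisation.

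**The population.** SAP 6.1: "The full analysis set (FAS) includes all consented and randomized subjects who have taken at least one dose of study medication". Protocol 8.1.1 and the synopsis agree. The sample-size paragraph of Protocol 5.1 is looser: the FAS "is defined as subjects who have taken at least one dose of study medication", with no mention of randomisation.

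**The gate.** Protocol 5.1: "Subjects who have reached an optimal dose will be randomized at Visit 5 to receive double-blind treatment". An optimal dose needs an ADHD-RS-IV reduction of at least 30%, a CGI-I of 1 or 2, and tolerability in the investigator's judgement. For everyone else, the synopsis says: "Subjects will be discontinued if they are unable to tolerate d-ATS or cannot reach their optimal dose by Week 5".

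**The competing rule.** SAP 7: "Summaries will be presented for the SP population for all subjects combined during the Dose-Optimization Period of the study". Yet SAP 6.3 gives the Safety population's purpose as dermal and safety endpoints.

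**The concern.** Two of the three tabulated scales, ADHD-RS-IV and CGI-I, decide who enters the FAS. Summarising their open-label values on the FAS conditions the result on its own outcome. Children who did not respond to d-ATS, or could not tolerate it, drop out of the tables that would show how it performed in those who started it.

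ADHD-RS-IV, CPRS-R:S and CGI are named under the secondary objectives, so these tables will be read. Because SAP 7.1 puts Visits 1 to 5 in the same d-ATS column as Visits 6 and 7, a reader may take the open-label figures as the response to be expected in any child who starts the patch. The SAP also gives two instructions on which population to use and does not say which governs.

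**Working it through.** The plan states no open-label response rate and no number entering dose optimisation, so there is no figure to reproduce. The check is textual, followed by an illustration of size.

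**1. Who is in the table.** The FAS requires randomisation and randomisation requires an optimal dose, so a child discontinued during dose optimisation is never in the FAS. Protocol 5.3.6 nevertheless collects ADHD-RS-IV and CGI-I at early termination. SAP 7 maps such scores to the next scheduled visit, and its worked example is a child who leaves after Visit 3. Under 7.1.3.3 and 7.1.3.5 that child's mapped scores reach no efficacy table.

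**2. What the gate forces.**
- *Visit at which the child qualified.* The gate needs CGI-I 1 or 2. SAP 4.2.5 counts 1, 2 or 3 as response. The first set lies inside the second, so every correctly randomised child is a CGI-I responder at that visit.
- *Visit 5.* Response is not forced. If a fraction d of FAS children had a later dose reduction and a fraction f of those lost the criterion, the rate is 1 − d × f. With d = 5% and f = 25% (assumed) it is 1 − 0.0125 = 98.8%. With d = 10% and f = 50% it is 95.0%. Scores can also worsen on an unchanged dose, so it could be lower.
- *Visits 1 to 3.* Dosing starts at the lowest strength and steps up weekly, so many FAS children will not yet have qualified. The table shows three assumed patterns of first qualification over Visits 1 to 4, as cumulative percentages of the FAS. Any first qualification at Visit 5 would lower them.

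| Share first qualifying at Visits 1/2/3/4 | Visit 1 | Visit 2 | Visit 3 | Visit 4 |
|---|---|---|---|---|
| Even: 25/25/25/25 | 25 | 50 | 75 | 100 |
| Late: 5/20/35/40 | 5 | 25 | 60 | 100 |
| Early: 40/30/20/10 | 40 | 70 | 90 | 100 |

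With all entrants as denominator, each entry is multiplied by R. The early pattern at R = 70% becomes 28, 49, 63 and 70.

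- *CPRS-R:S.* It is not part of the gate and has no responder definition. It is enriched only as far as it moves with the other two scales.

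**3. Size.** Let R be the share of entrants who reach an optimal dose, p(F) the response rate in the FAS and p(N) the rate in the rest. The all-entrant rate is R × p(F) + (1 − R) × p(N). If p(N) = 0, the ratio of the FAS rate to the all-entrant rate is 1/R. If p(N) lies between 0 and p(F), the ratio lies between 1 and 1/R. With 90 randomised and entrants = 90/R, rounded up:

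| R (assumed) | Entrants | Outside the FAS | 1/R |
|---|---|---|---|
| 95% | 95 | 5 | 1.05 |
| 90% | 100 | 10 | 1.11 |
| 80% | 113 | 23 | 1.25 |
| 70% | 129 | 39 | 1.43 |
| 60% | 150 | 60 | 1.67 |

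For the SAP's own CGI-I cut of 1 to 3, p(N) will probably exceed 0, because a child can be minimally improved without qualifying. There 1/R is an upper limit.

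**The case against.** The strongest reply is that SAP 7 already assigns dose-optimisation summaries to the Safety population, and its early-termination example shows that run-in dropouts were meant to be summarised. This stands in part. A reader might infer that open-label efficacy is settled as FAS-only, and the SAP does not support that as its single instruction. But the specific efficacy sections name the FAS, and SAP 6.3 does not list efficacy among the Safety population's uses. A programmer following 7.1.3.3 to 7.1.3.5 would build FAS tables.

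Second, failures are not hidden from the report. SAP 7.2 counts children enrolled into dose optimisation, those randomised, and the reasons for discontinuation. SAP 7.4.1 summarises dose by visit on the Safety population, and all data are listed. This stands: a reader can come close to R from disposition. It does not supply the ADHD-RS-IV or CGI-I summaries of those who left, nor an explicit count reaching the criterion.

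Third, following one randomised cohort from baseline to Visit 7 is a legitimate display. The open-label rows are descriptive and visibly uncontrolled, and no objective asks for an open-label response rate among entrants. That is a fair reason to keep FAS columns, provided they are labelled, but not to make them the only specified view.

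**Conclusion.** The point holds in bounded form. On the wording of SAP 7.1.3.3 to 7.1.3.5, open-label summaries are enriched for children who responded to and tolerated d-ATS, and this is unreconciled with SAP 7. Enrichment is complete for CGI-I response at the qualifying visit, likely close to that at Visit 5, smaller at Visits 1 to 3, and indirect for CPRS-R:S. A reader might infer near-complete response at every open-label visit. Stepwise titration rules that out as a consequence of the design.

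The inflation factor is at most 1/R, provided non-qualifiers respond no more often than FAS children. R is assumed because the documents do not give it. No particular mean change in ADHD-RS-IV can be derived: the spread of scores is not documented, and the SAP tabulates change from baseline without specifying percent change.

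Nor does the point impugn the trial's main result. The d-ATS versus placebo comparisons at Visits 6 and 7 are made among randomised children and keep their internal validity. They apply to children who met the optimal-dose criterion, which the design states openly. The issue is descriptive reporting and how far it generalises. It is worth correcting in the final SAP, before database lock.

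**What to change.** 1. Reconcile SAP 7 with 7.1.3.3 to 7.1.3.5. Tabulate and plot ADHD-RS-IV, CPRS-R:S and CGI-I at Visits 1 to 5 for all children dosed in dose optimisation (Safety population), apart from the double-blind table. Amend SAP 6.3 and 7.1 to match.
2. Include mapped early-termination scores for ADHD-RS-IV and CGI-I. The procedures in Protocol 5.3.6 do not list CPRS-R:S, so that table rests on scheduled visits.
3. Add the number and percentage reaching the optimal-dose criterion, with all entrants as denominator and withdrawals counted as not reached. This matters because a table of observed scores still loses children after they leave.
4. Keep the FAS for Visits 6 and 7. If open-label FAS columns stay as a cohort trajectory, label them as children who met the optimal-dose criterion.
5. State that the FAS definition in SAP 6.1 and Protocol 8.1.1 governs over the looser sentence in Protocol 5.1.

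Cost: SAP wording, a population flag and a few extra tables, with no new data. The open-label figures will look less favourable.

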### **5.3.6 *Early Termination***

If the subject is discontinued early (prior to Day 49), the following procedures will be performed:

1. Record any AEs or concomitant therapy since previous visit.
2. Perform drug accountability and collect all used and unused patches.
3. Obtain vital signs (sitting BP, HR, RR, oral body temperature).
4. Obtain weight.
5. Collect blood and urine for clinical laboratory assessments
  - Complete Blood Count (including differential and platelet count)
  - Blood Chemistry
  - Urinalysis
6. Perform a 12-lead electrocardiogram (ECG) prior to discharge.
7. Perform complete physical examination
8. Perform urine pregnancy testing on all female subjects of child-bearing potential.

Amendment 4: Version 5.0 May-08-2013

Amendment 3: Version 4.0 December-11-2012

Amendment 2: Version 3.0 October-31-2012

Amendment 1: Version 2.0 August-02-2012

Final Protocol May-25-2012

9. Obtain ADHD-RS-IV score.
10. Perform CGI-I.
11. Administration of the C-SSRS (Children's Since Last Visit version) by a trained staff member.
12. Dismiss from clinic.
13. Contact IVRS/IWRS to early discontinue the subject in the system.

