### **5.3.7 *ADHD Treatment after Study Completion or Early Withdrawal***

At the end of the study or at early withdrawal the investigator (in consultation with the subject/parent/caregiver) may resume the subject's usual ADHD treatment. In the event that the subject experiences intolerable side effects or the subject's ADHD symptoms worsen while in the study, the subject may be discontinued from the study and their usual ADHD treatment may be resumed at the discretion of the investigator (in consultation with the subject/parent/caregiver). The investigator may continue to provide up to 3 months care for behavior and medication management.

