3.1 SAMPLE SIZE CONSIDERATIONS

Assuming a standard deviation (SD) of [REDACTED] and based on an average difference in total SKAMP scores between Placebo and d-ATS of [REDACTED], 74 subjects would need to complete the study to detect a true difference of [REDACTED] in mean total SKAMP scores between placebo and d-ATS at 80% power when testing at a significance level of $\alpha = 0.05$ (2-sided). Assuming a dropout rate of 20%, 90 subjects will be randomized and it is expected that 74 subjects will complete the study. A subject will be considered to have completed the study if the subject received both treatments during the double-blind Treatment Period and have completed both 12-hour classroom sessions during the double-blind Treatment Period.

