7.1.2 Missing Data

MMRM is the best method to control type I error rate and minimize bias in the presence of missing data, although this does not fully overcome the issues and assumptions are still required to be made regarding the missing data mechanisms. Nevertheless, in the presence of a high drop out rate performance of sensitivity analysis is critical. The purpose of sensitivity analysis is to explore whether different analyses under different set of missingness assumptions provide robust efficacy results. The extent to which efficacy results are stable across such analysis provides confidence in the statistical conclusions.

Missing data can be considered to be missing completely at random (MCAR), missing at random (MAR), or missing not at random (MNAR) according to the National Academy of Sciences (2010).

To explore the effect of missing data the following sensitivity analyses will be conducted for the primary efficacy analysis for the FAS population. Under the assumption that missing data is missing at random and the analyses require the assumption of MAR to hold:

- Imputation based analysis
 - Multiple Imputation

Subjects with missing SKAMP total scores at any timepoint during Visits 6 and 7 will have these individual SKAMP total score values imputed.

Step 1: Imputation

For each missing SKAMP total score 20 imputations will be made using SAS PROC MI on the unimputed SKAMP total score efficacy data. All imputed data will be non-negative. For intermittent missing data the Markov Chain Monte Carlo (MCMC) simulation will be used, the number of burn in iterations will be set at 200, or higher if required for convergence. The thinning option will be set to select one out of every 100 iterations to ensure sufficient separation from previous iterations.

Once intermittent missing data has been imputed monotone missing data will be imputed using a regression model including factors for treatment and period and the SKAMP total score in the VAR statement.

The number of multiple imputations will be 20, leading to 20 completed data sets.

Step 2: Analysis of completed data sets

The imputed data for the primary endpoint will be analyzed as per the method described in section 7.1.1. This will lead to 20 estimates for the comparison of d-ATS with placebo.

Step 3: Inference

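### All three CGI-I treatment tests drop a child who leaves in Week 6, although the plan collects and maps that child's score; the comparison is biased if withdrawal depends on response and differs by treatment

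*SAP*

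**What the plan says.** SAP 7.1.3.5 gives the treatment comparison for CGI-I: "Differences between the treatment arms in the dichotomized versions of the CGI-I scores at Visits 6 and 7 will be analyzed by using McNemar's test". It adds two tests: "the Mainland-Gart test, which is a test of sequence versus period preference, will also be performed", and "Prescott's test, which extends the Mainland-Gart test by including subjects who show no preference between the two periods, will also be conducted". It promises test statistics and p-values, with no estimate or confidence interval, and does not say what happens to a child scored in one week only.

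Such a child does have a score. Protocol 5.3.6 opens with "If the subject is discontinued early (prior to Day 49), the following procedures will be performed", and CGI-I is on the list that follows. SAP 7 maps early-termination data to the next scheduled visit and treats the result as observed data before any summary or analysis. A Week 6 exit therefore becomes a Visit 6 score, and a Week 7 exit becomes a Visit 7 score.

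The FAS is the primary efficacy population and includes every randomised child with at least one dose (SAP 6.1, 7.1). The handling of missing data in SAP 7.1.2 is narrower: "To explore the effect of missing data the following sensitivity analyses will be conducted for the primary efficacy analysis for the FAS population". For comparison, double-blind ADHD-RS-IV data "will be analyzed in a similar way to the primary efficacy analysis, with the exclusion of timepoint from the model".

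**The concern.** The plan collects the Week 6 leaver's CGI-I, makes it analysable, and then names only tests that cannot use it. The FAS responder percentages and the CGI-I p-values would therefore describe different children. ADHD-RS-IV is also taken at early termination, but its model lets a one-period child contribute, and no reason is given for treating CGI-I differently.

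Withdrawal may well be related to response. Protocol 5.3.7 says that if "the subject's ADHD symptoms worsen while in the study, the subject may be discontinued from the study"; the same sentence also covers intolerable side effects. Every randomised child has reached an optimal d-ATS dose, which required response and tolerability, and half then go straight to placebo. Loss of placebo failures in Week 6 is therefore plausible. It would raise the apparent placebo response among complete pairs and pull the CGI-I difference toward zero. Loss of d-ATS failures would favour the drug.

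**Working it through.** **The plan's own figures.** SAP 3.1 states: "Assuming a dropout rate of 20%, 90 subjects will be randomized and it is expected that 74 subjects will complete the study". Check: 90 × (1 − 0.20) = 72, and 74 / (1 − 0.20) = 92.5, so 93. The stated figures agree with 20% only roughly; the implied loss is 16/90 = 17.8%. The 80% power behind 74 concerns SKAMP and cannot be recomputed, because the SD and difference are blacked out. No power is stated for CGI-I. The 16 expected non-completers are a ceiling for Week 6 leavers, since some will leave in Week 7 or miss only part of a classroom day.

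**Who reaches the tests.**

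| Path | Visit 6 CGI-I | Visit 7 CGI-I | FAS summaries | Paired tests |
|---|---|---|---|---|
| Completes | observed | observed | in | in |
| Leaves in Week 7 | observed | early-termination score | in | in |
| Leaves in Week 6 | early-termination score | none | in, first treatment only | out |

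**Size, under assumptions.** From the documents: 90 children, 1:1, so 45 per sequence if balanced. Assumed, because the documents give nothing: response 85% on d-ATS and 65% on placebo, and latent within-child correlation 0.3. These give four cell probabilities:

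- fails both: 0.08
- fails placebo, responds to d-ATS: 0.27
- responds to placebo, fails d-ATS: 0.07
- responds to both: 0.58

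Let wP and wD be the shares of placebo and d-ATS non-responders who leave in Week 6. Expected values are:

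- pairs favouring d-ATS: b = 45 × 0.27 × (1 − wP) + 45 × 0.27
- pairs favouring placebo: c = 45 × 0.07 + 45 × 0.07 × (1 − wD)
- complete pairs: k = 90 − 45 × 0.35 × wP − 45 × 0.15 × wD
- paired difference: (b − c) / k

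Example, wP = 0.5 and wD = 0.2: b = 6.08 + 12.15 = 18.23; c = 3.15 + 2.52 = 5.67; k = 90 − 7.88 − 1.35 = 80.8; difference = 12.56 / 80.8 = 0.155. With nobody leaving: (24.3 − 6.3) / 90 = 0.20.

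Power and the all-available results come from simulation (asymptotic McNemar, two-sided 0.05):

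| wP / wD | b | c | k | Paired difference | McNemar power | All-available difference | All-available power |
|---|---|---|---|---|---|---|---|
| 50% / 20% | 18.23 | 5.67 | 80.8 | 0.16 | 77% | 0.21 | 93% |
| 70% / 20% | 15.80 | 5.67 | 77.6 | 0.13 | 62% | 0.21 | 93% |
| 20% / 20% | 21.87 | 5.67 | 85.5 | 0.19 | 91% | 0.20 | 92% |
| 20% / 50% | 21.87 | 4.73 | 83.5 | 0.21 | 95% | 0.20 | 90% |

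The first two rows lose about 9 and 12 children. The standard error of the paired difference is about 0.057, so the shortfall from 0.20 is about 0.8 to 1.2 standard errors.

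**Second set of assumptions.** Response 60% against 80%, correlation 0.3, a set number of leavers, exact McNemar. With no leavers the difference is 20 points and power about 86%.

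| Week 6 leavers | Paired difference | Power |
|---|---|---|
| 8 placebo failures | 15 points | 58% |
| 8 d-ATS failures | 26 points | 98% |
| 4 of each | 21 points | 87% |

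**False positives.** With 75% response on both treatments and withdrawal of 60% of non-responders on one and 20% on the other, asymptotic McNemar rejects in about 9% of trials, whichever treatment loses more; the all-available model rejects in about 6%. With equal withdrawal both hold about 5%.

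**Scoring the missing week as failure does not help.** A child who failed in Week 6 becomes a fail/fail tie, which McNemar ignores. Under the second set of assumptions, power with 4, 8 or 16 placebo-failure leavers is 73%, 58% or 26% with or without that rule.

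**The case against.** The three tests suit paired binary crossover data. Week 6 leavers are not lost: their scores are mapped to Visit 6 and appear in the responder percentages by treatment, and SAP 7.2 reports discontinuation reasons by sequence, arm and period. Balanced withdrawal costs about one point of power (91% against 92%), and d-ATS-heavy withdrawal gives McNemar slightly more power than the model. The damaging settings need 50-70% of placebo non-responders to leave within a week. CGI-I is a secondary measure outside the closed testing procedure.

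Most of this stands, and it rules out several stronger readings that a reader might infer:

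- That these children cannot be scored, or that no rule covers them. The early-termination CGI-I and the mapping rule say otherwise; the gap is confined to the treatment tests.
- That the plan loses placebo failures, shrinks the difference and costs power. The documents give no dropout by treatment and foresee exit for side effects as well as worsening, so this is one plausible case only.
- That 16 of 90 children will be unpaired. That is a ceiling.
- That every other visit-level endpoint keeps these children. CPRS-R:S is due on Days 41 and 48 and is not an early-termination procedure, so a child leaving before Day 41 has no scheduled double-blind score for it. The contrast holds for ADHD-RS-IV.

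The objection does not explain why a collected, mapped score from an FAS child should enter no CGI-I comparison. The summaries show percentages but provide no treatment estimate or interval against which to judge a paired p-value from a selected subset.

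**Conclusion.** The point holds in limited form. Followed exactly, SAP 7.1.3.5 bases every CGI-I treatment test on children scored in both weeks, and no sensitivity analysis covers the rest. Bias arises if Week 6 withdrawal depends on response and differs by treatment. Its sign depends on who leaves, and equal withdrawal does little harm.

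Under the assumed 85% and 65%, placebo-heavy withdrawal takes a true 0.20 down to 0.16-0.13 and power to 77-62%, while d-ATS-heavy withdrawal (20%/50%) gives 0.21 and 95%. Response rates, correlation and withdrawal shares are all assumptions; the qualitative result needs only that withdrawal be selective and unequal. The change is worth making because it is cheap and CGI-I is a named secondary assessment. It does not touch the SKAMP conclusion.

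**What to change.** In SAP 7.1.3.5, add a binary repeated-measures model for dichotomised CGI-I (GEE or PROC GLIMMIX, logit link) with treatment, period and sequence, or treatment and period alone if sequence is aliased, and child as the cluster. Fit it to all FAS children with at least one double-blind CGI-I, including early-termination scores already mapped under SAP 7, and report the treatment estimate with its 95% CI. Keep McNemar, Mainland-Gart and Prescott on complete pairs, state that they are restricted to those pairs, and report the number of incomplete pairs by sequence and reason.

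The cost is some SAP wording and one extra model, with no new data or visits. The model relies on large-sample standard errors, and an available-data analysis is not exactly unbiased when withdrawal follows the Week 6 result (0.21 against a true 0.20 in the first two settings). The paired tests remain as a simple check.
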